5.1 Independent Data Monitoring Committee (IDMC)

Safety data will be periodically reviewed and evaluated by an IDMC at regular review meetings. The frequency will be based on the number of enrolled patients and will occur at least once every 3 months for the first year and every 6 months thereafter.

In addition, an IDMC safety review meeting is scheduled to occur once 10 patients in Arm 1 (BNT111+cemiplimab combination therapy) have been treated for at least two cycles (six weeks) or have discontinued treatment for any reason during the first 2 cycles.

[figure not shown]
Specific stopping criteria will be based on the cumulative incidence of trigger events (TEs). TEs include all related serious adverse events (SAEs), related Grade 3 to 5 TEAEs/irAEs except for transient Grade 3 flu-like symptoms, clinically insignificant laboratory abnormalities and Grade 3 hypotension lasting for less than 6 h.

Furthermore, the occurrence of a single grade 5 TEAE (unless clearly unrelated to study drug e.g., due to underlying disease) or a cumulative incidence of ≥ 40% of Trigger Events during the first two cycles of the first 10 patients in Arm 1 will trigger an ad hoc meeting of the IDMC as well as an enrollment pause.

Data presentations described in Sections 8.2, 8.3.1, 8.3.2, 8.3.3, 8.5.1, 8.5.2, 8.5.3 will be provided at each regular review IDMC meeting. Presentations provided for the safety review meeting and ad hoc meeting are described in the IDMC charter.

Page 21 of 78 Version: Final v7.0 Date: 05Mar2024

5.2 Interim analysis

IA2 will be performed after approximately of the planned number of patients are response evaluable (i.e., having at least two post-screening tumor assessments or discontinued before).

The operational characteristics of interim analysis (IA1 and IA2) of ORR are summarized in Section 8.4.1. Analysis for the BNT111 monotherapy and cemiplimab monotherapy arms as described in Section 8.4.2.1 will also be presented.

The minimal statistically significant ORR at IA2 will be column i.e., the smallest ORR that will result in a statistically significant p value of column in a statistical p value of column in

The final analysis for efficacy (i.e., the primary analysis of the trial) will be performed once all the planned patients in Arm 1 are response evaluable (i.e., having at least three post-screening tumor assessments or discontinued before). The minimal statistically significant ORR at final analysis would be cell i.e., the smallest ORR that will result in a statistically significant p value of

The following analyses have been provided at IA1.

- Analyses of ORR described in Section 8.4.2.6 using investigator assessment based on RECIST 1.1 and in Section 8.4.3.1 using investigator assessment based on iRECIST.
- Analyses of DOR described in Section 8.4.2.3 using BICR based on RECIST 1.1, in Section 8.4.2.6 using investigator assessment based on RECIST 1.1 and in Section 8.4.3.1 using investigator assessment based on iRECIST.
- Analyses of DCR described in Section 8.4.2.2 using BICR based on RECIST 1.1, in Section 8.4.2.6 using investigator assessment based on RECIST 1.1, in Section 8.4.3.1 using investigator assessment based on iRECIST.
- Analysis of TTR described in Section 8.4.2.4 using BICR based on RECIST 1.1, in Section 8.4.2.6 using investigator assessment based on RECIST 1.1, in Section 8.4.3.1 using investigator assessment based on iRECIST.
- Analysis of PFS described in Section 8.4.2.5 using BICR based on RECIST 1.1, in Section 8.4.2.6 using investigator assessment based on RECIST 1.1 and in Section 8.4.3.1 using investigator assessment based on iRECIST. For the first interim analysis only Kaplan-Meier plots were provided.
- Depth of response described in Section 8.4.3.2.

Page 22 of 78 Version: Final v7.0 Date: 05Mar2024

The following analyses will be provided at IA2:

- Subgroup analyses in Section 7.3 (the subgroup "Best response to prior PD-1 + CTLA-4 combination inhibitor therapy (CR, PR, SD, PD)" and "Best response to prior PD-1 inhibitor therapy (CR, PR, SD, PD)" are excluded.
- Analyses of ORR described in Section 8.4.3.5 using BICR based on RECIST 1.1, in Section 8.4.2.6/Section 8.4.3.5 using investigator assessment based on RECIST 1.1, in Section 8.4.3.1/Section 8.4.3.5 using BICR/investigator assessment based on iRECIST.
- Analyses of DOR described in Section 8.4.2.3/Section 8.4.3.5 using BICR based on RECIST 1.1, in Section 8.4.2.6/Section 8.4.3.5 using investigator assessment based on RECIST 1.1, in Section 8.4.3.1/Section 8.4.3.5 using BICR/investigator assessment based on iRECIST.
- Analyses of DCR described in Section 8.4.2.2/Section 8.4.3.5 using BICR based on RECIST 1.1, in Section 8.4.2.6/Section 8.4.3.5 using investigator assessment based on RECIST 1.1, in Section 8.4.3.1/Section 8.4.3.5 using BICR/investigator assessment based on iRECIST.
- Exploratory analysis of duration of disease control (DDC) in Section 8.4.3.2 using BICR/Investigator assessment based on RECIST 1.1 and in Section 8.4.3.3 using BICR/Investigator assessment based on iRECIST.
- Analysis of TTR described in Section 8.4.2.4/Section 8.4.3.5 using BICR based on RECIST 1.1, in Section 8.4.2.6/Section 8.4.3.5 using investigator assessment based on RECIST 1.1, in Section 8.4.3.1/Section 8.4.3.5 using BICR/investigator assessment based on iRECIST.
- Analysis of PFS described in Section 8.4.2.5/Section 8.4.3.5 using BICR based on RECIST 1.1, in Section 8.4.2.6/Section 8.4.3.5 using investigator assessment based on RECIST 1.1 and in Section 8.4.3.1/Section 8.4.3.5 using BICR/investigator assessment based on iRECIST.
- Depth of response described in Section 8.4.3.2.
- Analysis of Overall survival in Section 8.4.2.7/8.4.3.6
- Analysis of Biomarker data Section 8.4.3.8.1

[figure not shown]
6 SAMPLE SIZE DETERMINATION

The original sample size calculation for the BNT111+cemiplimab group (Arm 1) is based on the following specifications and assumptions:

Statistical Analysis Plan (SAP) BNT111-01

Page 23 of 78 Version: Final v7.0 Date: 05Mar2024

Page 24 of 78 Version: Final v7.0 Date: 05Mar2024

7 ANALYSIS SETS AND SUBGROUPS

7.1 Analysis sets

The following analyses sets are defined:

Table 7.1 Analysis Sets

Analysis Set	Description
Screened	The screened set is defined as all patients who signed informed consent.
Intent to treat	The Intent To Treat (ITT) set is defined as all patients who are randomized.
Modified intent to treat	The modified Intent To Treat (mITT) set is defined as all patients who are randomized, had at least one dose of trial treatment and have a baseline and at least one post-randomization tumor response assessment.
Add-on Treatment Set	The Add-on Treatment Set is defined as patients who received at least one dose of Add-on treatment
Safety	The safety set is defined as all patients who received trial treatment (i.e., at least one dose of BNT111 or cemiplimab).
Per protocol	The Per protocol Set (PPS) is defined as all patients who received trial treatment and fulfil the following criteria:
	 The absence of any important protocol deviations that could affect the primary efficacy analysis. The completion of a minimal exposure to the treatment of 1 cycle i.e. the patient should receive all the treatment doses planned as per schedule of assessment for at least 1 cycle. Availability of baseline and at least one on-treatment / post-randomization tumor assessment. Important deviations will lead to an exclusion of patients from the PPS and will be agreed at the data review meeting prior to database snapshot for the primary analysis.

7.2 Protocol deviations

Protocol deviations are failures to adhere to the inclusion/exclusion criteria and protocol requirements and will be classified into important protocol deviations (IPD) and non-important protocol deviations.

- IPDs are those that are considered to have a significant effect on the treatment efficacy and hence would exclude the patient from the Per protocol set.
- Non-important protocol deviations are those that are not considered to significantly affect the efficacy evaluation and hence do not warrant patients' exclusion from the Per protocol set.
- IPDs will be identified by medical review prior to unblinding/database snapshot for main analysis.

The following criteria might be considered as important protocol deviations:

Page 25 of 78 Version: Final v7.0 Date: 05Mar2024

- Violation of important inclusion or exclusion criteria
- Assignment to incorrect treatment/dose (i.e., actual treatment/dose taken differs from the randomized/scheduled)
- Non-compliance (i.e., relative dose intensity less than 80% or greater than 120%)
- Intake of prohibited concomitant medication/occurrence of prohibited medical procedures

IPDs will be presented in a listing. The number and percentage of patients with each IPD type will be summarized by treatment group. The number of patients excluded from the per protocol set will be summarized by treatment group.

7.3 Subgroups

Subgroup analyses will be performed for the primary endpoint (ORR based on BICR assessment using RECIST 1.1) and secondary endpoints DCR and PFS based on BICR assessment using RECIST 1.1. The analysis will be performed if the number of patients is substantial within each subgroup category. Substantial number of patients is defined as at least 10 patients in each of the subgroup categories for the BNT111 + cemiplimab treatment group. If there is a substantial number of patients for the BNT111 + cemiplimab treatment group then the analyses for the BNT111 and cemiplimab monotherapy treatment groups will be performed regardless of the number of patients in each subgroup category. The category "missing" will not be considered for the subgroup analysis.

The analysis will be performed for the BNT111 + cemiplimab, BNT111 and cemiplimab treatment groups using the CCI set.

The following subgroups, based on data collected before start of study treatment will be defined:

- Age group (Age < 70 years, Age ≥ 70 years)
- Sex (Male, Female)
- ECOG PS (ECOG PS 0, ECOG PS 1)
- BRAF mutation status (Mutated and Wild Type)
- Metastatic status ((M0, M1a, M1b), (M1c, M1d))
 - Number of prior therapy lines (1, 2 to 5). These subgroup categories will be identified from the prior cancer therapy CRF page.
- Anti-PD1 (programmed death protein 1) refractory/relapsed (Relapsed or refractory to prior PD-L1 treatment) (Yes, No)

These subgroup categories will be identified from the prior cancer therapy data by medical review. The categorization will be based on the last therapy line where anti-PD-1 or anti-PD-L1 was given. If the best response during the therapy is CR, PR or SD/non-PD (or disease status at the end of the therapy if best response is

Page 26 of 78 Version: Final v7.0 Date: 05Mar2024

missing) then the patient is considered as relapsed, otherwise it is considered as refractory.

If best response is "No evidence of disease" (or disease status at the end of the therapy if best response is missing) and if disease progression is within 3 months from end date of last line then it is considered refractory, otherwise it is relapsed (i.e. date of progression > last anti-PD-1/anti-PD-L1 end date + 3*30.4375). If the date of progression is partial and cannot be imputed then the patient will be excluded from the subgroup analysis.

Prior PD-1 inhibitor therapy (monotherapy, combination)

These subgroup categories will be identified from the prior cancer therapy data by medical review.

Prior BRAF/MEK inhibitor therapy (Yes, No)

These subgroup categories will be identified from the prior cancer therapy data using ATC codes.

Prior chemotherapy (Yes, No)

Chemotherapy will be identified from the prior cancer therapy data using ATC codes.

Brain metastasis (Yes, No)

This will be selected using Target Lesion Assessment and Non-Target Lesion Assessment data where sub-location = Brain

Visceral metastasis (Yes, No)

This will be identified using Target Lesion Assessment and Non-Target Lesion Assessment data based on BICR assessment. If any of the site/any lesion is reported as having "visceral location" then visceral metastasis =yes.

- Time since the first diagnosis (>median time since the first diagnosis vs <=median
 time since the first diagnosis). The median time since the first diagnosis will be
 derived by treatment group. Time since the first diagnosis will be calculated as:
 Date of informed consent Date of first diagnosis + 1.
- Sum of target lesion at baseline (>median sum of target lesions at baseline vs <=median sum of target lesions at baseline). The sum of target lesion at baseline will be derived by treatment group.
- Presence of liver metastasis (Yes, No) (target or non-target)

This will be identified using Target Lesion Assessment and Non-Target Lesion Assessment data based on BICR assessment. If any of the site/any lesion is reported as having "Liver location" then liver metastasis = yes.

In addition, the below subgroups will also be considered:

Use of systemic antibiotics (Yes, No)

Page 27 of 78 Version: Final v7.0 Date: 05Mar2024

Use of systemic antibiotics will be determined from the concomitant medication data. Use of systemic antibiotics during the treatment period will be checked.

Use of systemic corticosteroids (Yes, No)

Use of systemic corticosteroids will be determined from the concomitant medication data. Use of systemic corticosteroids during the treatment period will be checked.

- Occurrence of irAE during the treatment and Safety follow-up period (Yes, No)
- Best response to prior PD-1 inhibitor therapy (CR, PR, SD, PD)

Note: In case of re-challenge (≥2 PD1i treatment received by patient prior to enrolment) "best response to PD1i" is defined as best response to last PD-1 inhibitor therapy.

These subgroup categories will be identified from the prior cancer therapy data using ATC codes and best response to the therapy. Only patients who received PD-1 + CTLA-4 in combination will be included in this subgroup analysis:

 Best response to prior PD-1 + CTLA-4 combination inhibitor therapy (CR, PR, SD, PD)

The best response of the last PD-1 + CTLA-4 combination treatment taken before the first study trial treatment will be used.

Prior CTLA-4 inhibitor (yes, no)

These subgroup categories will be identified from the prior cancer therapy data and medical review.

Analysis detailed Sections 8.4.1, 8.4.2.1, 8.4.2.2 and 8.4.2.5 will be performed. All the subgroup analyses are exploratory, no adjustment for multiplicity will be performed. A p-value will not be presented.

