5.1 Inclusion and exclusion criteria

5.1.1 Inclusion criteria initial treatment

Patients are eligible to be included in the trial only if all the following general criteria apply:

- 1. Patients must sign the written ICF before any screening procedure.
- 2. Patients must be aged ≥ 18 years on the date of signing the ICF.
- 3. Patients must be willing and able to comply with scheduled visits, treatment schedule, laboratory tests, and other requirements of the trial.
- 4. Patients must have histologically confirmed unresectable Stage III or IV (metastatic) cutaneous melanoma and measurable disease by RECIST 1.1.
- 5. Patients must have confirmed disease progression on/after an approved anti-PD-1/PD-L1 regimen for melanoma as defined by RECIST 1.1
 - a. Previous exposure to approved anti-PD-1/PD-L1 containing regimen for at least 12 consecutive weeks **and**
 - Current radiological progression to be confirmed by two scans 4 to 12 wks apart. If progression is accompanied by new symptoms, or deterioration of PS not attributed to toxicity, one scan is sufficient and
 - c. Inclusion into this trial must be within 6 months of confirmation of disease progression on anti-PD-1/PD-L1 treatment, regardless of any intervening therapy
- 6. Inclusion criterion 6 was deleted.

Page 49 of 133 Version: 7.0 Date: 09 FEB 2023

- 7. Patients should have received at least one but no more than five lines of prior therapy for advanced disease (see Section 8.1.1 for definition of line of therapy).
- 8. Patients must be able to tolerate additional anti-PD-1/PD-L1 therapy (i.e., did not permanently discontinue anti-PD-1/PD-L1 therapy due to toxicity).
- 9. Patients must have known BRAF mutation status.
- 10. Patients with BRAF V600-positive tumor(s) should have received prior treatment with a BRAF inhibitor (alone or in combination with a MEK inhibitor).

Note: Considering the possible negative impact of a prior BRAF/MEK therapy on immune system targeting therapies, patients with BRAF V600-positive tumors with no clinically significant tumor-related symptoms or evidence of rapid PD may be eligible for participation. This should be based on investigator assessment AND provided they are ineligible for, intolerant to, or have refused BRAF V600 mutation targeted therapy after receiving the information on possible other therapies including BRAF/MEK inhibitor-based therapy during the informed consent process.

- 11. Patients must have an ECOG PS ≤ 1.

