8.1.1 Confirmation of anti-PD-1/PD-L1-refractory/relapsed patients

Patients should be resistant to prior anti-PD-1/PD-L1 therapy as specified by:

- a. Previous exposure to approved anti-PD-1/PD-L1 containing regimen for melanoma for at least 12 consecutive weeks **and**
- b. Current radiological progression to be confirmed by two scans 4 to 12 wks apart. If progression is accompanied by new symptoms, or deterioration of PS not attributed to toxicity, one scan is sufficient and
- c. Inclusion into this trial must be within 6 months of confirmation of disease progression on anti-PD-1/PD-L1 treatment, regardless of any intervening therapy.

The anti-PD-1/PD-L1 therapy may have been given in the (neo)-adjuvant or metastatic setting as long as resistance to anti-PD-1/PD-L1 therapy was confirmed. Patients should have received at least one line and not more than five lines of prior therapy. A line of therapy is defined as an anti-cancer regimen given until (confirmed) disease progression. The subsequent therapy given will be considered a new line of therapy. Interruption and reinitiation of a therapy due to toxicity will not be considered a new line.

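### When best response is missing, SAP 7.3 labels a relapser as refractory if the last anti-PD-1/PD-L1 line ended at progression

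*SAP*

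**What the plan says.** SAP 7.3 plans subgroup analyses of ORR, DCR and PFS (BICR, RECIST 1.1), one of them by relapsed or refractory status to prior anti-PD-1/PD-L1 treatment. On the line to be used it says: "The categorization will be based on the last therapy line where anti-PD-1 or anti-PD-L1 was given". The rule asks whether best response on that line was CR, PR or SD/non-PD. It gives a substitute in brackets, "or disease status at the end of the therapy if best response is", and continues over the page: "missing) then the patient is considered as relapsed, otherwise it is considered as refractory". A separate rule, with a three-month limit, covers patients whose best response was no evidence of disease. The categories are to be identified by medical review of the prior cancer therapy data.

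Two protocol passages determine what end status can be:
- Section 8.1.1: "A line of therapy is defined as an anti-cancer regimen given until (confirmed) disease progression".
- Section 5.1.1, criterion 5: "Patients must have confirmed disease progression on/after an approved anti-PD-1/PD-L1 regimen for melanoma as defined by RECIST 1.1".

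Criterion 8 of the same section admits only patients who "did not permanently discontinue anti-PD-1/PD-L1 therapy due to toxicity". That removes one common reason for a line to end without progression.

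**The concern.** The subgroup is meant to separate patients who once had disease control on PD-1 blockade from those who never did. Best response carries that information. Status at the end of a line given until progression does not: it is PD for both kinds of patient. Using it as the substitute decides the label by how the line ended, and the label is always refractory.

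At stake is how the exploratory results are read. Protocol 4.2 describes the target population in terms of primary and secondary resistance, and this subgroup is where efficacy is shown along that division. If relapsers sit in the refractory group, its ORR, DCR and PFS describe a mixture, and the difference between the two groups is diluted.

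**Working it through.** The plan states no figure for this point, so there is none to reproduce. The check applies the rule to each case and then gives an illustrative size.

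**1. The rule, case by case**

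| True best response | Status at end of line | Label if best response recorded | Label if best response missing |
|---|---|---|---|
| CR, PR or SD | PD | relapsed | **refractory (wrong)** |
| CR, PR or SD | CR or SD (stopped before progression) | relapsed | relapsed |
| PD | PD | refractory | refractory |

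The error occurs only in the first row and only in one direction.

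**2. Inputs for size**
- Arm 1: 90 patients (SAP Table 3.2).
- Share of relapsers, s. Protocol 4.2 gives 40 to 45% primary and 30 to 40% secondary resistance. So s runs from 30/(30 + 45) = 0.40 to 40/(40 + 40) = 0.50. This counts initial responders; the SAP also counts SD as relapsed, so s could be higher.
- Share of Arm 1 with missing best response and end status PD, u. The documents do not give it. Assumed 0.05 to 0.15, and taken as unrelated to the true response.

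**3. Formulas**
- Mislabelled relapsers = 90 × u × s
- True refractory = 90 × (1 − s), that is 54 at s = 0.40 and 45 at s = 0.50
- Share of the labelled refractory group that is mislabelled, c = mislabelled / (true refractory + mislabelled)

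**4. Results**

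| u | s | Mislabelled | c |
|---|---|---|---|
| 0.05 | 0.40 | 90 × 0.05 × 0.40 = 1.8 | 1.8/55.8 = 3.2% |
| 0.05 | 0.50 | 90 × 0.05 × 0.50 = 2.25 | 2.25/47.25 = 4.8% |
| 0.15 | 0.40 | 90 × 0.15 × 0.40 = 5.4 | 5.4/59.4 = 9.1% |
| 0.15 | 0.50 | 90 × 0.15 × 0.50 = 6.75 | 6.75/51.75 = 13.0% |

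With u = 0 nobody is mislabelled.

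**5. Effect on the contrast**

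Let R and F be the ORR in true relapsers and true refractory patients, and suppose the mislabelled respond like other relapsers. The labelled refractory group then shows (1 − c)F + cR, and the relapsed-minus-refractory difference becomes (1 − c)(R − F). It shrinks by c, that is by 3 to 13% of its true value.

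**The case against.** - **Medical review.** A reviewer sees the prior-therapy data, and SAP 8.3.3 summarises time on anti-PD-1/PD-L1 before progression and time from stopping to progression. A patient with more than a year on therapy would stand out. Some cases may be caught this way, but the written rule gives the reviewer no override and no other source.
- **Not every line ends at progression.** Criterion 5 allows progression after the regimen, Protocol 8.1.1 allows (neo)adjuvant therapy, and SAP 8.3.3 provides for progression more than six months after stopping. This stands and limits the scope: for such lines the substitute is harmless or falls under the rule for no evidence of disease.
- **Another subgroup uses best response directly.** SAP 7.3 also plans a subgroup by best response to prior PD-1 inhibitor therapy, with no substitute stated. It is a useful cross-check but does not correct the label here, and SAP 5.2 leaves it out of the second interim analysis.
- **The effect is small.** If the two groups' ORR differed by 15 points (an assumption), the refractory ORR would move by about 0.5 to 2 points (0.032 × 15 to 0.130 × 15). An exact 95% interval on about 50 patients reaches roughly 10 points or more either side. This stands.
- **An internal contradiction?** A reader might infer that the substitute conflicts with the statement in SAP 7.3 that missing categories are not considered. The text does not support that. The statement can be read as applying to a category still missing after derivation; the substitute is part of the derivation and recurs in the rule for no evidence of disease.

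**Conclusion.** The rule as written gives a wrong label to a definable set of patients: true relapsers whose last anti-PD-1/PD-L1 line ended at progression and whose best response is missing. That follows from the text and needs no assumption. The size does. About 2 to 7 Arm 1 patients, or 3 to 13% of the refractory group, rests on an assumed 5 to 15% with missing best response and end status PD, on a relapser share taken from a general statement in Protocol 4.2, and on missingness unrelated to response. The true number could be near zero.

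A reader might infer that refractory results would look better than they are. That needs relapsers to respond better to this combination, which the documents do not show; what is supported is a mixed group and a blurred contrast. A reader might also infer a threat to the trial's main conclusion. There is none: relapsed/refractory status is neither an objective nor a stratification factor, the subgroups are exploratory without p-values, and the primary ORR analysis does not use this label.

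**What to change.** In SAP 7.3, reword the substitute for a missing best response:
- If end-of-therapy status is itself CR, PR or SD/non-PD, classify as relapsed, since that shows disease control.
- Leave the time-based rule for no evidence of disease as it is.
- If end-of-therapy status is PD or also missing, treat the patient as missing and leave them out of this subgroup.
- Report the number left out by arm.

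The cost is a short SAP edit and a small programming change. The downside is that some correctly labelled refractory patients drop out too. Under the assumptions above, 90 × 0.05 = 4.5 to 90 × 0.15 = 13.5 Arm 1 patients would be left out, of whom 50 to 60% are truly refractory. That is a modest loss from one exploratory subgroup, and close to none if best response is nearly always recorded.

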Treatment and trial duration	Patient level: Patients will receive treatment BNT111 + cemiplimab or BNT111 or cemiplimab, single agents up to 24 months and will continue until unacceptable toxicity, withdrawal of consent, discontinuation due to investigator's decision or (confirmed) disease progression. The duration of therapy for patients entering into add-on therapy is a total of 24 months for both the monotherapy and add-on therapy part. Trial level: Approximately 18 months of recruitment followed by approximately up to 48 months
	of OS follow-up from the randomization of last patient.
Planned number of patients	180 patients will be randomized overall (90 patients to Arm 1 (BNT111 + cemiplimab) and 45 patients each to calibrator Arms 2 (BNT111 mono), and 3 (cemiplimab mono).
Randomization and	Automated centralized randomization.
blinding	Stratification factors: metastatic status: M0, M1a, M1b versus M1c, M1d and by number of prior lines of systemic treatment (1 vs 2 to 5) Treatment Allocation Ratio: 2:1:1 Blinding: Open-label
Tumor assessment schedule:	Tumor response assessments will be performed at screening, every 6 (±1) weeks for the first 3 months after randomization, then every 9 (±1) weeks for the next 9 months and every 12 (±2) weeks thereafter. Until (confirmed) disease progression, death, withdrawal of consent, or until the start of next-line anti-cancer therapy, whichever occurs earlier. Tumor response will be assessed by investigator as well as by blinded independent central review (BICR) of radiographic images and will be measured using RECIST 1.1 and iRECIST.
	The same schedule will be followed if a patient receives Add-on treatment.
Other features	Per the IDMC charter, regular meetings by an IDMC will be scheduled to review and evaluate safety data. Details on the meeting frequency are described in Section 5.1. of this SAP. Review of Interim analysis will occur per Section 5.2 of this SAP.

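### Two exploratory median-split subgroups take their cut-point from each arm separately, so their labels need not mean the same thing across arms

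*SAP*

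**What the plan says.** SAP Section 7.3 lists the subgroups for ORR, DCR and PFS by central review. Two continuous variables are split at a median.

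- **Time since first diagnosis.** The split is above the median against at or below it. The next sentence begins "The median time since the first diagnosis will be" and goes on to say that this is done by treatment group. The arm-specific cut is explicit.
- **Baseline tumor burden.** The split is "Sum of target lesion at baseline (>median sum of target lesions at baseline vs <=median sum of target lesions at baseline". The following sentence is "The sum of target lesion at baseline will be derived by treatment group". It names the sum, not the median.

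The results are produced in every arm: "The analysis will be performed for the BNT111 + cemiplimab, BNT111 and cemiplimab treatment groups using the" analysis set, whose name is redacted. The size condition is "at least 10 patients in each of the subgroup categories for the BNT111 + cemiplimab treatment group", with no minimum in Arms 2 and 3. Table 3.2 gives the arm sizes: "180 patients will be randomized overall (90 patients to Arm 1 (BNT111 + cemiplimab) and 45 patients each to calibrator Arms 2" and 3.

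Section 7.3 also says that all subgroup analyses are exploratory and carry no p-value. Section 8.1 rules out formal comparison between arms, but in its paragraph on time-to-event endpoints it leaves room for an exploratory one. Randomization is stratified by metastatic status and number of prior lines (Section 3.2), not by either of these two variables.

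**The concern.** A subgroup label should describe the patient. With an arm-specific median it also depends on who else was allocated to that arm. Sample medians in arms of 90 and 45 will differ by chance even when the arms are alike, and any value lying between two arms' medians gets opposite labels in those arms.

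The rule is also out of line with the rest of Section 7.3. Age has one cut at 70 years in every arm, and the categorical subgroups are defined identically in every arm.

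What is at stake is descriptive reading across arms. Section 3.2 says that the single-agent arms are there to delineate what each component contributes, so readers will look at high-burden ORR in Arm 1 next to high-burden ORR in Arms 2 and 3. Tumor burden is of particular interest here: Protocol Section 4.2 justifies the eligibility criteria by the better prospects of a vaccine when burden is low.

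**Working it through.** **1. Which variables are affected.** The diagnosis-time sentence needs no interpretation. The lesion sentence does. A patient's sum of diameters does not depend on the arm, so deriving the sum by arm has no literal meaning. Read with the bullet before it, the workable meaning is that the median of the sums is taken by arm. For this variable the point is an inference from loose wording.

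**2. Inputs.** Allocation is 2:1:1 of 180 patients, so 180 × 2/4 = 90 and 180 × 1/4 = 45 in each calibrator arm, matching Table 3.2. The documents give no distribution for either variable. Assumption: lognormal, identical in all arms, with the SD of the log between 0.6 and 1.0. The plan states no figure of its own to reproduce here.

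**3. Hand check of the chance difference.** On the log scale, in SD units, the standard error of a median is about √(π/2)/√n. For Arm 1 against one calibrator arm:

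SE of difference = 1.253 × √(1/90 + 1/45) = 1.253 × 0.183 = 0.229 SD.

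The mean absolute difference is 0.229 × √(2/π) = 0.229 × 0.798 = 0.183 SD. Near the median the normal density is 0.399 per SD, so the share of patients between the two cuts averages about 0.183 × 0.399 = 7.3%.

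**4. Simulation (90/45/45, identical arms, simple random sampling).**

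| Quantity | Result |
|---|---|
| Share between the Arm 1 and Arm 2 cuts | mean about 7%, 90th percentile about 15% |
| Share between the lowest and highest of the three cuts | mean about 11%, 90th percentile about 19% |
| Calibrator-arm patients who change class against a pooled cut | mean about 5% (0.05 × 45 ≈ 2 patients) |
| Arm 1 patients who change class against a pooled cut | mean about 3% |
| Trials with at least 10% (5 or more of 45) changing class in at least one calibrator arm | about 23% |
| Largest to smallest arm median, log-SD 0.6 | typically 1.18, 90th percentile about 1.34 |
| Same, log-SD 0.9 | typically 1.27, 90th percentile about 1.56 |
| Same, log-SD 1.0 | typically 1.30, 90th percentile about 1.64 |

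The shares do not depend on the assumed SD; the ratios do. The simulation ignores stratification. Metastatic status is probably related to tumor burden, so the true chance differences for that variable may be somewhat smaller.

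**5. Does a pooled cut cost feasibility?** With one median over all 180 patients, the number of Arm 1 patients above the cut has a 95% range of 38 to 52 of 90, and a calibrator arm 17 to 28 of 45. The Arm 1 minimum of 10 per category was met in every simulated trial. Discordance across arms is zero by construction.

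**The case against.** The strongest reply is that the plan does not rest on cross-arm subgroup reading. Efficacy is analyzed by treatment group, the calibrator ORR is descriptive (SAP Sections 4 and 8.4.2.1), no formal comparison is made, and the subgroups carry no p-values. A high/low contrast within one arm is a legitimate purpose in itself. It stays valid with an arm-specific median, which also keeps each arm split almost evenly. The exploratory comparison in Section 8.1 is optional and does not mention subgroups. All of this stands.

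The effect is also small beside ordinary sampling error. Four responders among 22 patients give an exact 95% interval of 5% to 40%. In an illustration with ORR near 20% and a logistic burden effect of 0.7 per SD (both assumed), the Arm 1 minus Arm 2 difference in low-burden ORR had an SD of 11.7 percentage points under either cut, with mean bias of at most 0.4 points. Changing the cut moved an individual trial's difference by an SD of about 3.7 points. Subgroup size matters more than the cut-point rule.

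A reader might therefore be tempted to infer that these subgroup results cannot be set against the calibrator arms at all, or that such a comparison is the only reason to show them. The documents support neither: about 95% of a calibrator arm keeps its class on average, and the within-arm purpose is genuine. What remains is that two of the listed subgroups carry labels that vary by arm, for no stated benefit.

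**Conclusion.** The point holds as a minor matter of interpretability. It is certain from the text for time since first diagnosis and a reasonable inference for the lesion sum. The arm-specific cut complicates descriptive reading of ORR, DCR and PFS across arms for these two exploratory subgroups and no others. About 5% of a calibrator arm changes class on average against a pooled cut, and in about 23% of trials at least 10% of a calibrator arm does. These shares assume identical distributions and unstratified sampling at 90/45/45. The ratio of arm medians, typically 1.18 to 1.30, also depends on an assumed log-SD of 0.6 to 1.0. If the arms truly differed, more patients would be affected: with true medians in a ratio of 1.2 or 1.5 and log-SD 0.8, about 9% or 19% would fall between the cuts.

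It should not be read as an error-rate problem. The primary Arm 1 ORR test, its type I error and the within-arm contrasts are unaffected.

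**What to change.** In SAP Section 7.3, for each of the two variables, compute one median over all randomized patients in the analysis set, pooled across the three arms, and apply it in every arm. Reword the lesion sentence so that it refers to the median of the baseline sums. Section 5.2 also schedules these subgroup analyses at the second interim analysis, so any output already made with arm-specific cuts should carry a footnote giving the cut used in each arm.

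The cost is a sentence per variable and a line of code. No new data, visits or patients are needed.
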